9.10 Auditing Procedures

Regulatory or ethics authorities of domestic and foreign agencies, Sponsor QA and [REDACTED], Inc. Quality Assurance and/or its designees may carry out on-site inspections and/or audits to evaluate compliance with the protocol and GCP principles. Access to the original source data may be required for inspections and/or audits. All inspections and audits will be carried out giving consideration to data protection as well as subject confidentiality to the extent that local, state, and federal laws apply.

If an inspection is requested by a regulatory authority or IRB/EC, the investigator must inform the sponsor and [REDACTED] immediately of the request.

10 ADVERSE EVENTS

10.1 Adverse Event

An AE is defined as any untoward medical occurrence associated with the use of an IP in humans, whether or not considered IP-related. An AE can be any unfavorable and unintended sign (e.g., an abnormal laboratory finding), symptom, or disease with onset following the signing of informed consent through study exit, that is temporally associated with the use of an IP, without any judgment about causality. An AE can arise from any use of the IP (e.g., off-label use, use in combination with another drug or medical device) and from any route of administration, formulation, or dose, including an overdose.

All AEs spontaneously reported by the subject and/or in response to an open question from study personnel or revealed by observation, physical examination, or other diagnostic procedures will be recorded in the subject's source document and eCRF.

An AE can also include a progression/worsening of an underlying disease, hypersensitivity and extravasation. Any clinically relevant deterioration in clinical findings is considered an AE and must be recorded. When possible, signs and symptoms indicating a common underlying pathology should be noted as one comprehensive event or diagnosis.

Documentation regarding the AE should be made as to the nature, date of onset, end date, severity, relationship to IP, expectedness, action(s) taken, seriousness, and outcome of any sign or symptom observed by the physician or reported by the subject upon indirect

questioning.

At the time of informed consent, a subject's current and relevant medical history will be collected. At subsequent visits through the study exit visit, any AEs that are new and AEs (or Medical History events) that have worsening will collect severity and date of onset. Additionally, all AEs will be reviewed for dates of resolution, when applicable.

10.1.1 Severity

The severity of an AE is defined as a qualitative assessment of the degree of intensity of an AE as determined by the investigator or reported to him/her by the patient/subject. The assessment of severity is made irrespective of relationship to IP or seriousness of the event and should be evaluated according to the following scale:

- *Mild*: Event is noticeable to the subject, but is easily tolerated and does not interfere with the subject's daily activities.
- *Moderate*: Event is bothersome, possibly requiring additional therapy, and may interfere with the subject's daily activities.
- *Severe*: Event is intolerable, necessitates additional therapy or alteration of therapy, and interferes with the subject's daily activities.

10.1.2 Relationship to Investigational Product

The relationship of each AE to the IP should be determined by the investigator using these explanations:

- *Suspected*: A reasonable possibility exists that the IP caused the AE.
- *Not Suspected*: A reasonable possibility does not exist that the IP caused the AE.

“Suspected adverse reaction” means any AE for which there is a reasonable possibility that the IP caused the AE. “Reasonable possibility” means there is evidence to suggest a causal relationship between the IP and the AE. Types of evidence that would suggest a causal relationship between the IP and the AE include: a single occurrence of an event that is uncommon and known to be strongly associated with IP exposure (e.g. angioedema, hepatic injury, Stevens-Johnson Syndrome); one or more occurrences of an event that is not commonly associated with IP exposure, but is otherwise uncommon in the population exposed to the IP (e.g. tendon rupture); an aggregate analysis of specific events observed in a clinical trial (such as known consequences of the underlying disease or condition under investigation or other events that commonly occur in the study population independent of drug therapy) that indicates those events occur more frequently in the IP-treatment group than in a concurrent or historical control group.

10.1.3 Expectedness

The expectedness of an AE should be determined based upon existing safety information about the IP using these explanations:

- *Unexpected*: an AE that is not listed in the Investigator's Brochure (IB) or is not listed at the specificity or severity that has been observed.
- *Expected*: an AE that is listed in the IB at the specificity and severity that has been observed.

- *Not applicable:* an AE unrelated to the IP.

AEs that are mentioned in the IB as occurring with a class of products or as anticipated from the pharmacological (or other) properties of the product but are not specifically mentioned as occurring with the particular product under investigation are to be considered unexpected.

The investigator should initially classify the expectedness of an AE. The medical monitor will review and determine the expectedness of any serious adverse event (SAE) following the investigator's assessment. The final classification of an AE is subject to the sponsor's determination.

10.2 Serious Adverse Events

An AE is considered serious if, in the view of either the investigator or sponsor, it results in any of the following outcomes:

- Death;
- A life-threatening AE;
- Note: An AE is considered “life-threatening” if, in the view of either the investigator or sponsor, its occurrence places the patient or subject at immediate risk of death. It does not include an AE that, had it occurred in a more severe form, might have caused death.
- Inpatient hospitalization or prolongation of existing hospitalization;
- Note: The term “inpatient hospitalization” refers to any inpatient admission (even if < 24 hours). For chronic or long-term inpatients, inpatient admission includes transfer within the hospital to an acute/intensive care inpatient unit. Inpatient hospitalization does not include: emergency room visits; outpatient/same-day/ambulatory procedures; observation/short stay units; rehabilitation facilities; hospice facilities; nursing homes; or clinical research/Phase 1 units.
- Note: The term “prolongation of existing hospitalization” refers to any extension of an inpatient hospitalization beyond the stay anticipated or required for the reason for the initial admission as determined by the investigator or treating physician.
- A persistent or significant incapacity or substantial disruption of the ability to conduct normal life functions;
- Note: An SAE specifically related to visual threat would be interpreted as any potential impairment or damage to the subject's eyes (e.g., intra-ocular hemorrhage, retinal detachment, central corneal ulcer, or damage to the optic nerve).
- A congenital anomaly/birth defect.

Important medical events that may not result in death, are life-threatening, or require hospitalization may be considered serious when, based upon appropriate medical judgment, they may jeopardize the patient or subject and may require medical or surgical intervention to prevent one of the outcomes listed in this definition.

10.3 Procedures for Reporting Adverse Events

All AEs and their outcomes must be reported to [REDACTED], the study sponsor, and the IRB as required by the IRB, federal, state, or local regulations and governing health authorities and recorded on the appropriate subject source document and eCRF.

10.3.1 Reporting a Suspected Unexpected Adverse Reaction

All AEs that are ‘suspected’ and ‘unexpected’ are to be reported to [REDACTED], the study sponsor, and the IRB as required by the IRB, federal, state, or local regulations and governing health authorities.

10.3.2 Reporting a Serious Adverse Event

To ensure subject safety, all SAEs, regardless of relationship to the IP, must be immediately reported by the investigator to [REDACTED] and the sponsor within 24 hours of becoming aware of the event. All information relevant to the SAE must be recorded on the appropriate source document, SAE Report Form, and eCRF. The investigator is obligated to pursue and obtain information requested by [REDACTED] and/or the sponsor in addition to the information reported on the source document, SAE Report Form, and eCRF. All subjects experiencing a SAE must be followed-up with and the outcome reported.

In the event of a SAE, the investigator must notify the study Medical Monitor immediately; obtain and maintain in his/her files all pertinent medical records, information, and medical judgments from colleagues who assisted in the treatment and follow-up of the subject; provide [REDACTED] and the study sponsor with a complete case history, which includes a statement as to whether the event was or was not suspected to be related to the use of the IP; and inform the IRB of the AE within their guidelines for reporting SAEs.

10.4 Procedures for Unmasking

When medically necessary, the investigator may need to determine what treatment has been assigned to a subject.

In an emergency situation, where knowledge of the study drug treatment is critical to the study safety, the code may be broken. Study Treatment should remain masked to the CRO, study monitor (CRA) and Sponsor.

The Investigator should determine if the situation is a medical emergency (ocular or non-ocular) and whether the knowledge of the treatment is critical to subject safety. The Investigator should attempt to contact the Medical Monitor prior to unmasking the study treatment if possible. If unmasking is necessary, only the Primary Investigator will have the appropriate level of access in order to perform the unmasking within the [REDACTED] Clinical One Interactive Response Technology (IRT) System. The Primary Investigator will select the subject, follow the prompts to “Manage Subject” and then select the “Code Break” option. During this process, the Primary Investigator will be asked to confirm each step as well as whether the unmasking is related to an adverse event. Once all confirmatory questions are answered, the subject’s treatment arm will be unblinded and the treatment arm will be displayed for the subject along with the assigned kits. For step-by-step details on Emergency Unmasking procedures, please refer to the IRT Training Plan.

The investigator must notify the Medical Monitor and the Study Monitor as soon as possible after unmasking. In addition, the Investigator must record the date, time and

reason for unmasking the study drug treatment in the source documentation, however, the subject treatment must NOT be recorded in the source documents. The unmasked subject must be discontinued from study.

10.5 Type and Duration of the Follow-up of Subjects after Adverse Events

The investigator will follow unresolved AEs to resolution, until the subject is lost to follow-up or until the AE is otherwise explained. Resolution means the subject has returned to baseline state of health or the investigator does not expect any further improvement or worsening of the AE. If the subject is lost to follow-up, the investigator should make 3 reasonable attempts to contact the subject via telephone, post, or certified mail. All follow up will be documented in the subject's source document. Non-serious AEs identified on the last scheduled contact must be recorded on the source document with the status noted.

If the investigator becomes aware of any new information regarding a SAE (i.e., resolution, change in condition, or new treatment), a new SAE Report Form must be completed and faxed/mailed to [REDACTED] and/or the study sponsor within 24 hours. The original SAE Report Form is not to be altered. The SAE Report Form should describe whether the event has resolved or continues and how the event was treated.

11 STATISTICAL HYPOTHESES AND METHODS OF ANALYSES

11.1 General Considerations

In general, quantitative/continuous data will be summarized using descriptive statistics (number of subjects [n], mean, standard deviation [SD], median, minimum, and maximum).

Qualitative/categorical data will be summarized using frequencies and percentages. Statistical testing, unless otherwise indicated, will be performed at a 2-sided 0.05 significance level.

For all variables, baseline is defined as the last measurement taken prior to the administration of the first dose of study drug. Change from baseline will be calculated as follow-up measure minus baseline measure.

Summaries and listings will be presented for all subjects, or safety set, as needed. Safety analyses will be conducted in the safety set.

11.2 Analysis Sets

- Safety Set – The safety set will include all randomized subjects who have received at least 1 dose of the study drug. Subjects in the safety set will be analyzed as treated and will be used for the safety analyses. No data will be excluded for any reason.
- Unit of Analysis

Both eyes will be displayed and analyzed for all ophthalmic safety variables.

11.3 Safety Endpoints

The safety endpoints are:

- AEs (reported, elicited, and observed)

- Vital signs (resting blood pressure and pulse) at Visit 1 Screening and Visit 4 - Week 6 or next scheduled visit (study exit) for subjects treated beyond Visit 4 at the time of Protocol Amendment 2.0 approval
- Physical exam (general health, head, eyes, ears, nose, throat, and other comments) at Visit 1 Screening, Visit 4 - Week 6 or next scheduled visit (study exit) for subjects treated beyond Visit 4 at the time of Protocol Amendment 2.0 approval
- BDCVA
- LL-BDCVA
- Slit lamp biomicroscopy
- Fluorescein staining
- IOP
- Dilated indirect fundus exam at Visit 1 Screening, Visit 4 - Week 6 or next scheduled visit (study exit) for subjects treated beyond Visit 4 at the time of Protocol Amendment 2.0 approval

Systemic labs at Visit 1 Screening, Visit 4 - Week 6 or next scheduled visit (study exit) for subjects treated beyond Visit 4 at the time of Protocol Amendment 2.0 approval

11.4 Sample Size

Approximately 170 subjects will be randomized into the study in a 2:1 ratio of CSF-1:vehicle [approximately 113 randomized subjects assigned to CSF-1 and approximately 57 subjects randomized to vehicle] completing at least 6 weeks of treatment. Any subjects treated beyond Visit 4 at the time of Protocol Amendment 2.0 approval will exit the study at the next scheduled visit. All subject data will be analyzed.

11.5 Demographic and Baseline Characteristics

Subject demographics including age, gender, race, ethnicity, and iris color will be presented using continuous/categorical summary statistics as appropriate.

11.6 Safety Analysis

All safety data will be analyzed using the safety set. Safety of CSF-1 compared to vehicle will be assessed by the review of all safety parameters.

Verbatim descriptions of AEs will be mapped to Medical Dictionary for Regulatory Activities (MedDRA) terms and be presented in a data listing. Treatment emergent AEs (TEAEs) is defined as any event not present prior to the initiation of the drug treatment or any event already present that worsens in either intensity or frequency following exposure to the drug treatment. TEAEs will be summarized by treatment group using frequency and percent for each system organ class (SOC) and preferred term (PT) within each SOC. The

number of AEs, TEAEs, serious TEAEs, and TEAEs causing premature discontinuation will be provided by treatment group. In addition, the frequency and percentage of subjects with at least one AE, at least one TEAE, and at least one serious TEAE will also be provided by treatment group.

Similar summaries will also be presented for TEAEs related to the study drug, by severity, and by study day of onset. When reporting the incidence of AEs, a subject will only be counted once if they ever experience an event within the SOC and ever experience the individual PT within each treatment group. The number of AEs as well as the incidence rate over the study period will also be summarized.

Changes from baseline in vital signs, BDCVA, LL-BDCVA, slit lamp biomicroscopy, IOP, and dilated indirect fundus examination and endothelial cell density will be summarized descriptively for at each visit by treatment group. Changes from baseline in endothelial cell density parameters will be tested between treatment groups using two-sample t-tests.

The categorical summaries for the loss of ≥ 0.2 logMAR from baseline (yes/no) and for the loss of > 0.2 logMAR (yes/no) in BDCVA and LL-BDCVA at each visit will also be presented and compared between treatment groups using Pearson chi-squared test or Fisher's exact test if any cell counts are less than 5.

Full details of the safety analyses will be specified in the formal Statistical Analysis Plan.

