Dosage/Dose Regimen/ Instillation/Application/Use:	Enrolled subjects will be randomized 2:1 to receive CSF-1 or vehicle bilaterally. Subjects will be instructed to dose one drop in each eye, twice daily (BID), at 2 to 3 hours intervals (OU). This regimen should be followed daily.. Subjects who have not completed Visit 4 (Week 6) at the time of Protocol Amendment 2.0 approval will dose for at least 6 weeks. Subjects treated beyond Visit 4 at the time of Protocol Amendment 2.0 approval will dose until the next scheduled visit and exit the study. Subjects must avoid dosing prior to visit on the day of a visit. If subjects dose prior to their visit, the study visit will be rescheduled.
Summary of Visit Schedule:	
• Visit 1 (Day -30 to Day -7): Screening;• Visit 2 (Week 1/Day 1): Baseline Assessments;• Visit 3 (Week 2/Day 15 ± 2 days): Safety Assessments;• Visit 4 (Week 6 + 7 days): Safety Assessments & Exit;• Visit 5 (Week 12 ± 7 days): Safety Assessments & Exit Visit (for all subjects who have completed Visit 4 at the time of Protocol Amendment 2.0 approval)• Visit 6 (Week 18 ± 7 days): Safety Assessments & Exit Visit (for all subjects who have completed Visit 5 at the time of Protocol Amendment 2.0 approval)• Visit 7 (Week 21 ± 7 days): Safety Assessments & Exit Visit (for all subjects who have completed Visit 6 at the time of Protocol Amendment 2.0 approval)
Measures Taken to Reduce Bias:	Randomization will be used to avoid bias in the assignment of subjects to treatment and to enhance the validity of statistical comparisons across treatment groups. Double-masked treatment will be used to reduce potential of bias during data collection the evaluation of clinical endpoints.

Randomization will be at a 2:1 ratio (CSF-1:Vehicle).	
Study Population Characteristics:	
Number of Subjects:	This study will enroll approximately 170 subjects (approximately 113 subjects assigned to CSF-1 and approximately 57 subjects assigned to vehicle) treated for at least 6 weeks. All subjects treated beyond Visit 4 at the time of Protocol Amendment 2.0 approval will exit the study at the next scheduled visit ([REDACTED]).
Condition/Disease:	Healthy adult subjects ages 40 to 64 years who have presbyopia

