A sample size of 113 subjects treated with CSF-1 for at least 6 weeks will have at least 95% probability of detecting adverse events that occur at a rate of 2.66% or greater.

Safety Analysis

All safety data will be analyzed using the safety set. Safety of CSF-1 compared to vehicle will be assessed by the review of all safety parameters.

Verbatim descriptions of AEs will be mapped to Medical Dictionary for Regulatory Activities (MedDRA) terms and be presented in a data listing. A treatment-emergent adverse event (TEAE) is any event not present prior to the initiation of the drug treatment or any event already present that worsens in either intensity or frequency following exposure to the drug treatment. TEAEs will be summarized by treatment group using frequency and percent for each system organ class (SOC) and preferred term (PT) within each SOC. The number of AEs, TEAEs, serious TEAEs, and TEAEs causing premature

discontinuation will be provided by treatment group. In addition, the frequency and percentage of subjects with at least one AE, at least one TEAE, and at least one serious TEAE will also be provided by treatment group.

Similar summaries will also be presented for TEAEs related to the study drug, by severity, and by study day of onset. When reporting the incidence of AEs, a subject will only be counted once if they ever experience an event within the SOC and ever experience the individual PT within each treatment group. Number of AEs by a set interval of time will be summarized for each interval. Or number of AEs will be summarized for set intervals of time..

Changes from baseline in BDCVA, LL-BDCVA, slit lamp biomicroscopy, fluorescein staining, IOP, and dilated indirect fundus examination will be summarized descriptively at each visit where performed by treatment group.

The categorical summaries for the loss of ≥ 0.2 logMAR from baseline (yes/no) and for the loss of > 0.2 logMAR (yes/no) in BDCVA and LL-BDCVA at each visit will also be presented and compared between treatment groups using Pearson chi-squared test or Fisher's exact test if any cell counts are less than 5.

Full details of the safety analyses will be specified in the formal Statistical Analysis Plan (SAP).

Summary of Known and Potential Risks and Benefits to Human Subjects

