5 OVERALL STUDY DESIGN

This is a 4 visit, multi-center, double-masked, vehicle-controlled study evaluating the long-term safety of CSF-1 compared to vehicle in a total of approximately 170 subjects with presbyopia (approximately 113 subjects assigned to CSF-1 and approximately 57 subjects

[REDACTED]

[REDACTED]

[REDACTED]

[REDACTED] All subjects who have not completed Visit 4 at the time of Protocol Amendment 2.0 approval will proceed with the scheduled visits until study exit at Visit 4 (Week 6). All subjects treated beyond Visit 4 at the time of Protocol Amendment 2.0 approval [REDACTED] will proceed to study exit at the next scheduled study visit ([REDACTED]). The maximum timepoint for these subjects to exit the study will be Visit 7 (Week 21). All subject data will be analyzed for all measured timepoints, including data from subjects treated beyond Visit 4.

Subjects will be consented and study eligibility will be determined at Visit 1 (Screening). Subjects who remain eligible after Visit 1 will return for Visit 2 (Baseline Visit) to be assessed for randomization into the study. If eligible, subjects will be enrolled in this safety study and randomized 2:1 to receive CSF-1 or vehicle bilaterally. All study treatments are topical ophthalmic solutions that should be administered bilaterally. The initial dose will be instilled during Visit 2 after completing the visual acuity assessment. Subjects will be instructed to instill with a single drop in each eye (OU) twice daily (BID) at approximately 2-to-3-hour intervals later. Subjects would be reminded not to dose at home on clinic visit days. Medical history updates and adverse event assessments will be done at this and subsequent visits. Investigational product and dosing diary will be dispensed to subject. Subject will be instructed to return to clinic at the next scheduled visit.

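### AE percentages pool 6 to 21 weeks of follow-up with no fixed window, and AE counts per interval show no number at risk

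*Combined protocol and SAP*

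**What the plan says.** **Exit rule.** Subjects who had not completed Visit 4 when Amendment 2.0 was approved exit at Week 6. For the others, the Synopsis (Dosage/Dose Regimen) says: "Subjects treated beyond Visit 4 at the time of Protocol Amendment 2.0 approval will dose until the next scheduled visit and exit the study". The visit schedule makes that Week 12, 18 or 21, and Section 5 sets Week 21 as the latest exit. Visit 4 has a window of plus 7 days.

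**Data used.** Section 5: "All subject data will be analyzed for all measured timepoints, including data from subjects treated beyond Visit 4". Section 11.4 also says that all subject data are analysed.

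**AE percentages.** Section 11.6 plans, by treatment group, "the frequency and percentage of subjects with at least one AE, at least one TEAE, and at least one serious TEAE". No time window is given.

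**Time-related summaries.** Section 11.6 and the Synopsis both include this sentence: "Similar summaries will also be presented for TEAEs related to the study drug, by severity, and by study day of onset". Section 11.6 then adds: "The number of AEs as well as the incidence rate over the study period will also be summarized". In its place the Synopsis has two near-identical sentences: "Number of AEs by a set interval of time will be summarized for each interval", followed by "Or number of AEs will be summarized for set intervals of time". Neither section gives interval lengths, numbers at risk or a denominator for the rate.

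**Sizing.** The Synopsis ties its precision statement to 6 weeks of treatment: "A sample size of 113 subjects treated with CSF-1 for at least 6 weeks will have at least 95% probability" of detecting AEs that occur at a rate of 2.66% or more.

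Both sections leave full details to a formal SAP, whose text is not in the documents available for this review.

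**The concern.** Safety against vehicle is the only objective, so absolute AE risks and their pattern over time are the main output. A percentage pooled over subjects followed for 6, 12, 18 or 21 weeks has no common time base. Its value depends on how many subjects happened to be past Visit 4 on the approval date, which the readable text does not state. AE counts per interval shrink as subjects leave, so a table showing fewer AEs in later weeks could be taken to mean that AEs subside with continued use. No planned table limited to a window shared by all subjects appears in the readable text.

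**Working it through.** **1. The plan's own figure.** With n = 113 and p = 0.0266, the chance of at least one event is 1 − (1 − 0.0266)^113 = 95.25%. The rule of three gives 3/113 = 2.655%. The 2.66% reproduces and is not in dispute.

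**2. Pooled percentage.** The exit weeks (6, 12, 18, 21) come from the Synopsis and Section 5. The rest is assumed: a 10% risk by Week 6, four exit mixes, and the hazard after Week 6. The 90/5/3/2 mix is closest to the duration of about 6 weeks in Section 9.8; equal quarters is an upper extreme.

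λ = −ln(0.9)/6 = 0.01756 per week to Week 6, then kλ, with k = 1 (constant), 0.5 (halved) or 0 (all onset early).

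Risk by week t = 1 − exp(−[6λ + kλ(t − 6)]).

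For k = 1 the risks at Weeks 6, 12, 18 and 21 are 10.0, 19.0, 27.1 and 30.8%. The pooled percentage is their mix-weighted mean. For 90/5/3/2: 0.90 × 10.0 + 0.05 × 19.0 + 0.03 × 27.1 + 0.02 × 30.8 = 11.4%.

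| Exit mix at Weeks 6/12/18/21 (%) | k = 1 | k = 0.5 | k = 0 |
|---|---|---|---|
| 90/5/3/2 | 11.4% | 10.7% | 10.0% |
| 70/10/10/10 | 14.7% | 12.5% | 10.0% |
| 50/20/20/10 | 17.3% | 13.8% | 10.0% |
| 25/25/25/25 | 21.7% | 16.2% | 10.0% |

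The 6-week risk is 10% in every cell.

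**3. Interval counts.** Assume a constant 0.02 AEs per subject-week among 113 CSF-1 subjects. Expected count = 0.02 × number at risk × 6 weeks. Weeks 0–6: 0.02 × 113 × 6 = 13.6 in every mix.

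| Exit mix (%) | At risk, Weeks 6–12 | AEs, Weeks 6–12 | At risk, Weeks 12–18 | AEs, Weeks 12–18 |
|---|---|---|---|---|
| 90/5/3/2 | 11.3 | 1.4 | 5.65 | 0.7 |
| 70/10/10/10 | 33.9 | 4.1 | 22.6 | 2.7 |
| 50/20/20/10 | 56.5 | 6.8 | 33.9 | 4.1 |
| 25/25/25/25 | 84.75 | 10.2 | 56.5 | 6.8 |

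From the first interval to the second the count falls by 90, 70, 50 or 25%, although the rate never changes.

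**4. Would one overall subject-time rate be enough?** Mean subject-weeks at risk of a first event, for exit at t, are 0.1/λ + 0.9 × (1 − exp(−kλ(t − 6)))/(kλ), or 0.1/λ + 0.9 × (t − 6) when k = 0. The overall rate is the pooled risk divided by mix-weighted subject-weeks. Per 100 subject-weeks, in the order of the mixes above:

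- k = 1: 1.76 in all four
- k = 0.5: 1.65, 1.47, 1.37, 1.27
- k = 0: 1.52, 1.15, 0.97, 0.76

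A single rate is free of the exit mix only under constant hazard.

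**5. Where to cut the common window.** Visit 4 may fall up to 7 days after Week 6. Under constant hazard, a subject seen at Week 7 has risk 1 − 0.9^(7/6) = 11.6% rather than 10%. That shift is about as large as the one in the 90/5/3/2 mix, so a cut-off at the visit date does not give a common window; a fixed study day does.

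**The case against.** **Onset-day summaries.** Nobody exits by rule before Week 6, so apart from withdrawals every subject is followed to that point, and the planned onset-day summaries can locate events before it. This partly stands. They show when events began, but the readable text states no boundary at Week 6 and no number still followed afterwards.

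**The SAP may settle this.** It may. Lines in Section 5 are also redacted, and Cohort, a stratification factor in Section 9.1.6, is not defined in the readable text. The point therefore rests on the method as written in the protocol.

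**The incidence rate may already be per subject-time.** That reading is natural, because percentages of subjects are promised separately. The term is undefined rather than wrong, and step 4 shows that one overall rate would not be enough.

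**The Synopsis and Section 11.6 differ only editorially.** This stands. The two Synopsis sentences say nearly the same thing, and both sections' outputs can be produced. That is housekeeping.

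**The sizes are assumed.** This stands. The documents give no exit mix, AE risk or hazard shape, and with all onset early the pooled percentage is not shifted at all.

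Three stronger readings are tempting, and the documents do not support them:

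- *Bias between arms.* The exit rule is the same in both randomised arms, and randomisation is stratified by Cohort. Even a large imbalance, with 40% of one arm and 60% of the other staying past Week 6 (spread equally over the later exits), gives 16.3% against 19.4% at constant hazard with a 10% Week 6 risk.
- *A rate split at Week 6 is always free of the exit mix.* This needs a constant hazard after Week 6. If the hazard holds to Week 12 and then drops to zero, the rate after Week 6 is 1.12, 0.98, 1.06 and 0.98 per 100 subject-weeks across the four mixes.
- *Thin later intervals undermine the sizing statement.* That statement covers subjects treated for at least 6 weeks and promises nothing for later intervals.

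**Conclusion.** The concern holds for absolute AE risk and its pattern over time, and only for those. As written, the overall percentages mix four lengths of follow-up and the Synopsis interval counts have no number at risk. With an assumed 10% Week 6 risk, the pooled percentage runs from 10% (all onset early) to about 22% (constant hazard, equal quarters), and is about 11% if few subjects go past Week 6. A reader of the final tables could not tell which case applied. No systematic distortion of the comparison between arms is expected. The change is worth making because it is cheap and bears on the trial's main output; confidence is medium because the exit mix is unknown and the SAP could not be read.

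**What to change.** (a) Alongside the all-data tables, add a treatment-emergent AE table by arm limited to onset from first dose through a fixed study day equal to 6 weeks, for example Day 42 (6 × 7 days, first dose on Day 1). Do not use the Visit 4 date as the cut-off. State the number of subjects in each arm who withdrew before that day.

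(b) In any AE summary by interval or by onset day, use fixed intervals with a boundary at that day, and show number at risk and subject-time for each interval and arm.

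Housekeeping: keep one of the two duplicate Synopsis sentences, align it with Section 11.6, and say whether the incidence rate is per subject or per subject-time.

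Cost: wording in the Synopsis and Section 11.6, or in the SAP, plus a few tables. Section 10.1 already requires the onset date of each AE. Visits, sample size and data collection do not change.
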